13.3.2 Interim Analyses for Toxicity

Under the same model described for futility, toxicities will be monitored assuming a prior probability of toxicity following $\text{Beta}(0.6, 1.4)$ in the current treatment arm against a constant rate of 0.30. Based on a previous study, we assume that a 15% rate of toxicity events would be acceptable and a 30% rate of toxicity would be unacceptable. [68] For trial monitoring and decisions about future trials, extreme toxicities (TOX) will be defined as any grade 3 or higher adverse event that is possibly, probably, or definitely related to any therapy received on this protocol and occur between the first dose of Durvalumab and surgery (or 4 weeks after that dose if the patient does not receive surgery as scheduled) with the following exception. Any grade 3 adverse event that is

potentially treatable with steroids will only count as an extreme toxicity if it does not improve to grade 2 or better within 2 weeks. Grade 3 nausea or vomiting that responds to anti-emetics within 72 hours and asymptomatic grade 3 or 4 lipase or amylase elevations will not count as TOX. The trial will be terminated if $\text{Prob}(\Theta_{\text{TOX}} > 0.30 | \text{data}) > 0.9$, where Θ_{TOX} is the proportion of patients experiencing a TOX event. Following this rule, the trial will be terminated according to the following table once the first 3 patients are evaluable.

If there are this many patients (or more) with TOX	3	4	5	6	7	8	9	10	11
Stop the cohort if there are this many (or fewer) patients who are evaluable (have TOX or completed 4 weeks after first Durvalumab dose without TOX)	3	7	9	12	14	17*	20	22	25*

* Always stop with 25 patients in Cohort A, but if 11 or more patients have TOX, then this treatment regimen is too toxic for further use. Always stop at 15 patients in Cohorts B and C, but if 8 or more patients have TOX, then this regimen is too toxic for further use.

Three patients in each cohort will be accrued first. If 3 of the 3 patients have TOX, stop that cohort and the treatment will be declared as too toxic for that cohort. If there is at least 1 patient with surgery without TOX, the next patient will be entered in the study, unless the trial needs to stop according to futility boundaries above. Check continuously as described above for toxicity assuming the trial does not stop for futility first. The operating characteristics for the combined futility and toxicity are summarized in the following table

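### The first entry of the pre-surgery toxicity stopping table should be 4, not 3: the plan's own rule stops a cohort at 3 TOX in 4 patients, but the table lets it continue

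*Combined protocol and SAP*

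**What the plan says.** Section 13.3.2 monitors TOX with a Beta(0.6, 1.4) prior "in the current treatment arm against a constant rate of 0.30". A cohort stops when the posterior probability of a rate above 0.30 is greater than 0.9. The table is presented as the working form of that criterion: "Following this rule, the trial will be terminated according to the following table once the first 3 patients are evaluable".

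The upper row of the table is headed "If there are this many patients (or more) with TOX" and lists 3 to 11. The lower row gives the number of evaluable patients at or below which the cohort stops: "Stop the cohort if there are this many (or fewer) patients who are evaluable (have TOX or completed 4 weeks after first Durvalumab dose". Its entries are 3, 7, 9, 12, 14, 17, 20, 22 and 25. The text below describes only the first look: "If 3 of the 3 patients have TOX, stop that cohort and the treatment will be declared as too toxic for that cohort".

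Section 13.3 starts monitoring at 3 evaluable patients, makes it continuous from there, and has the tables consulted before each new patient consents. Four evaluable patients is therefore a decision point. The operating-characteristics table that closes Section 13.3.2 combines this rule with the surgery futility rule of Section 13.3.1, for N = 25 (Cohort A) and N = 15 (Cohorts B and C).

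**The concern.** The table should list, for each TOX count, the largest number of evaluable patients at which the posterior criterion is still met. Under 3 TOX it lists 3, so a cohort with 3 TOX among 4 patients is told to continue. If the criterion is already met at 3 of 4, rule and table give opposite instructions at the earliest point where they can differ, and the table is what is checked before each consent.

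The missed stop is not necessarily recovered at the next look. If the fifth patient is free of TOX, the count is 3 of 5, which no longer meets the criterion. The reported operating characteristics would also describe a different design from the one the table carries out.

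**Working it through.** **Inputs.** From 13.3.2: prior Beta(0.6, 1.4), reference rate 0.30, cutoff 0.9, and the printed boundaries. From 13.3.1: prior Beta(1.2, 0.8) for the surgery rate, with a stop if the posterior probability of a rate below 0.60 exceeds 0.90. From 13.3: looks from the third evaluable patient onward. From the operating-characteristics table: toxicity and surgery independent, N = 25 or 15.

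**Formula.** After x TOX in n evaluable patients the posterior is Beta(0.6 + x, 1.4 + n − x). The boundary for x is the largest n with Pr(rate > 0.30) > 0.90.

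**Boundaries from the rule.**

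| TOX | Printed n | Posterior at boundary n | Posterior at next n | n from the rule |
|---|---|---|---|---|
| 3 | 3 | 0.935 (n = 4) | 0.875 (n = 5) | **4** |
| 4 | 7 | 0.901 | 0.846 | 7 |
| 5 | 9 | 0.922 | 0.880 | 9 |
| 6 | 12 | 0.905 | 0.865 | 12 |
| 7 | 14 | 0.925 | 0.893 | 14 |
| 8 | 17 | 0.914 | 0.883 | 17 |
| 9 | 20 | 0.906 | 0.876 | 20 |
| 10 | 22 | 0.924 | 0.899 | 22 |
| 11 | 25 | 0.918 | 0.894 | 25 |

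At 3 of 3 the posterior probability is 0.976. At 3 of 4 the posterior is Beta(3.6, 2.4) and the probability is 0.935, well clear of 0.90, so rounding does not explain the entry. The futility boundaries in 13.3.1 and the post-surgery boundaries in 13.3.3 all reproduce.

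**Sensitivity.** Treating the 0.30 reference as an informative beta with mean 0.30 (total weight 100 to 100,000) gives 0.930 to 0.935 at 3 of 4. Priors Beta(1, 1), Beta(0.5, 0.5) and Beta(0.3, 0.7) give 0.953 to 0.970. No variant removes the stop.

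**Operating characteristics.** I enumerated the joint design exactly, with looks from n = 3 to N − 1, for all 20 scenarios and both sample sizes (40 cells).

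| Boundary under 3 TOX | Pr(stop early) matching print | Means matching | Quartile sets matching |
|---|---|---|---|
| 4 | 40 of 40 | 40 of 40 | 38 of 40 |
| 3 (printed) | 13 of 40 | 8 of 40 | 23 of 40 |

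The two quartile misses with boundary 4 are both at toxicity 0.50 and surgery 0.60, where the 75th percentile comes out as 13 against 12 printed.

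Two examples:
- Toxicity 0.50, surgery 0.80, N = 25. The plan prints mean 10.7 and quartiles 4 and 16. Boundary 4 gives 10.71, 4 and 16; boundary 3 gives 11.22, 6 and 17.
- Toxicity 0.50, surgery 0.50, N = 15. The plan prints mean 7.3. Boundary 4 gives 7.32; boundary 3 gives 7.68.

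**A check without software.** Under the printed tables no cohort can stop at exactly 4 patients. Four TOX in 4 implies 3 in the first 3, and no surgery in 4 implies none in the first 3, so either would already have stopped the cohort. Yet the plan prints a lower quartile of 4 in ten cells: toxicity/surgery 0.40/0.50, 0.50/0.50, 0.50/0.60, 0.50/0.70 and 0.50/0.80, at both sample sizes.

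**How often it matters.** For a true rate p, the chance of 3 TOX in the first 4 without 3 in the first 3 is 3p³(1 − p), ignoring futility stops. From that state the printed table next stops at 4 TOX in 7 or fewer, so the chance of a toxicity stop by patient 7 is 1 − (1 − p)³. The product of the first quantity and (1 − p)³ is the chance of reaching the state and still being open on toxicity after patient 7.

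| True TOX rate | Reaches 3 of 4 | Then stops by patient 7 | Reaches it and is still open after patient 7 |
|---|---|---|---|
| 0.15 | 0.9% | 38.6% | 0.5% |
| 0.30 | 5.7% | 65.7% | 1.9% |
| 0.40 | 11.5% | 78.4% | 2.5% |
| 0.50 | 18.8% | 87.5% | 2.3% |

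**The case against.** The arithmetic is not in dispute; the size of the consequence is. Four points can be made in the plan's favour.

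- The next column of the printed table usually catches the cohort. After 3 of 4, any TOX in patients 5 to 7 triggers a stop, so few cohorts escape altogether. This stands, and the last column of the table above shows it.
- Averages barely move. Over the 40 cells the two boundaries differ by at most 0.015 in the probability of early stopping and 0.51 patients in mean size. Section 13.3 already accepts one or two patients beyond the boundary because enrollment does not wait. The small average stands. The tolerated overrun, however, is about the delay in applying a boundary and does not justify a wrong boundary.
- The posterior rule is printed correctly just before the table and again at the head of the operating-characteristics table, and Section 13.4 adds review of a toxicity report by the IND Office. But the table is the working tool before each consent, and nothing in the text exempts 3 of 4. The sentence on 3 of 3 is correct as far as it goes; it simply stops at the first look.
- Cohort A had 14 patients at the point of surgery by June 2018 (Section 2.6) and about 25 were expected by approval of this revision (Section 13.2). The exposure going forward is therefore mainly in Cohorts B and C. This also stands.

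**Conclusion.** The concern holds. Under the stated prior, reference rate and cutoff, the boundary for 3 TOX is 4 evaluable patients, and the printed 3 is wrong. The other eight entries are right. The operating characteristics were evidently computed with 4, so the cell looks like a transcription slip and not a design choice.

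The practical effect is confined to one state, 3 TOX among 4 evaluable patients. Its probability is 5.7% at the rate the plan calls unacceptable (0.30) and rises to 18.8% at 0.50. In most such cohorts the error delays a stop by one to three patients; in about 2% of all cohorts at true rates of 0.30 to 0.50 the cohort is still open on toxicity after patient 7. These figures assume a look after every evaluable patient and independent outcomes with a constant TOX rate, and the reaching probabilities ignore futility stops. The effect on average performance is small. The correction is still required, because this is a safety decision table that contradicts the rule it is meant to apply.

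**What to change.** In the Section 13.3.2 table, change the entry under 3 TOX from 3 to 4, so that the lower row reads 4, 7, 9, 12, 14, 17, 20, 22, 25. In the paragraph below it, add that 3 TOX among the first 4 evaluable patients also stops the cohort.

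The stopping probabilities and means in the operating-characteristics table already belong to the corrected boundary and need no change. The two 75th percentiles at toxicity 0.50 and surgery 0.60 (12 printed, 13 by exact enumeration) can be checked against the software output at the same time.

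The cost is one cell and one sentence in an amendment, with no added patients, data or simulation.

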One of the major research questions in immunotherapy—and checkpoint inhibitor therapy in particular—is establishing why only a subset of patients responds. Early data point to overall mutation burden as a key factor. More research is needed in this area to help delineate biomarkers of response and, ultimately, to choose the best candidates for what can be toxic therapy. A pre-operative approach will allow biomarker discovery and validation as tissue will be available before and after the therapy is given. MD Anderson—through the Immune Platform—has the capability and expertise to optimize such discovery.

As of 6-1-2018 this clinical trial (2015-0828) has enrolled 18 patients of which 2 screen failed, 2 have been treated but not yet reached the point of surgical resection, and 14 patients have undergone therapy and reached the point of surgical liver resection. Eleven of these 14 patients, 79%, have undergone liver resection, which is similar to the historical rate of 80%, and demonstrates this neoadjuvant approach to be safe. Treatment toxicity did not preclude any patient from undergoing surgery, with the reasons for non-surgery being progression in two patients and underlying prior chemotherapy induced liver toxicity in one patient. Grade 3/4 reported toxicities were fatigue (n=1), thromboembolic event (n=1), lipase elevation (n=1) and AST/ALT increase (n=3). Given the demonstrated safety of this approach we have amendment the protocol to evaluate the safety of other novel immune therapy combinations and thus, this study will explore the safety of three immunotherapy based approaches all utilizing durvalumab

as the consistent agent. In part, the rationale for exploring additional combinations rests upon the early clinical signals of activity with these other immune therapy agents in solid cancer and especially colorectal cancer. In addition, at this time after 15 patients enrolled, the safety of such a preoperative immune therapy approach has been determined. The translational knowledge gained from the combination of durvalumab and tremilimumab has clearly demonstrated T-cell activity with this combination occurs and, at present, greater knowledge gained from the translational aspects of this clinical trial will be best optimized by exploring additional immune therapy combinations prior to liver resection.

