10. STUDY CALENDAR AND SCHEDULES

Table 10.1 Study Calendar from Enrollment until Surgical Resection

TIME PERIOD	Screening	Wk	Wk	Comment
		1	4**	
	within 14 days	+/-3d	3 - 10 weeks**	
PROCEDURE				
Cohort A: Tremelimumab + Durvalumab		X		
Cohort B: Durvalumab + Oleclumab		X		
Cohort C: Durvalumab + Monalizumab		X		
Liver/lung resection			X	
Clinic Visit	X	X	X	
Physical Examination	X	X	X	
Vital Signs	X	X	X	Including BP, HR, temperature. Obtain vital signs
Review of Concomitant Medication	X	X	X	
Laboratory	X	X	X	CBC w/differential and platelet count, LFTs (ALT, AST, total bilirubin, alkaline phosphatase), BUN or serum urea level, creatinine, Ca, Mg, Na, K, Cl, glucose)
CEA lab		X	X	
HIV and hepatitis and PT/PTT	X (within 30 days allowed)			HIV, hepatitis B and C testing and PT/PTT
Specialized laboratory tests	X		X	Lipase, amylase, TSH, FT4
Pregnancy test (WOCBP only)	X	X		Serum or urine pregnancy test to be done within 72 hours prior to first dose.
ECOG PS	X	X	X	see appendix 1
Adverse Events Assessment	X		X	Per CTCAE v4.03 for Cohort A and v5.0 for Cohorts B and C
CT C/A/P with IV contrast with tumor measurements	X (within 30 days)		X	
Immunogenicity Assessment (special lab)		X	X	
Liver biopsy (tumor)	X			
Immuno- genicity Assessments, Peripheral Blood		12 red top tubes of blood with 5ml each will be collected for immunological assessment. See section 5.1.3 (up to 4 missed blood draws are allowed)		
**Factoring the occurrence of potential immune mediated adverse events prior to resection, an allowance of 3 - 10 weeks after the administration of neoadjuvant therapy will be permitted to complete metastatic and/or primary resection.				

CEA: Carcinoembryonic Antigen; ECOG PS: Eastern Cooperative Oncology Group Performance Status; TSH: Thyroid stimulating hormone; FT4: Free T4; WOCBP: Women of child bearing potential; CT C/A/P: CT scan chest, abdomen and pelvis

Table 10.2 Post-Resection Study Calender for Cohort A (Durvalumab + Tremelimumab)

(Week 1 begins the day Durvalumab treatment is given)

TIME PERIOD	Post-operative evaluation	Wk	Wk	Wk	Wk	Wk	Comment
		1	5	9	13	every 4months	
	(0.5-2wks post surgery)	+/-3d	+/-7d	+/-7d	+/-7d	+/-6 weeks	
PROCEDURE							
Durvalumab		X	X	X	X		If patient requires >12 weeks for postop recovery, they will not be initiated on adjuvant immunotherapy
Clinic Visit	X	X	X	X	X	X	
Physical Examination	X	X	X	X	X	X	
Vital Signs	X	X	X	X	X	X	Including BP, HR, temperature
Review of Concomitant Medication	X	X	X	X	X		

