Laboratory	X	X	X	X	X	X	CBC w/differential and platelet count, LFTs (ALT, AST, total bilirubin, alkaline phosphatase), BUN or serum urea level, creatinine, Ca, Mg, Na, K, Cl, glucose)
CEA	X			X		X	
TSH/FT4	X			X			
Lipase/amylase	X						
Immunogenicity Assessments, Peripheral Blood	X				X	X (at first visit only)	

Pregnancy test (WOCBP only)		X	As indicated clinically						Serum or urine pregnancy test to be done within 72 hours of dose				
ECOG PS	X	X	X	X	X			see appendix 1					
Adverse Events Assessment	X	X	X	X	X			Per CTCAE v4.03 for Cohort A and v5.0 for Cohorts B and C					
CT C/A/P with IV contrast with tumor measurements					X	X							
Immunogenicity Assessments, Peripheral Blood	Up to 12 tubes of blood with 5ml each will be collected for immunological assessment. For specific details see laboratory manual (up to 4 missed blood draws are allowed)												
	
CEA: Carcioembryonic Antigen; ECOG PS: Eastern Cooperative Oncology Group Performance Status; TSH: Thyroid stimulating hormone; FT4: Free T4; WOCBP: Women of child bearing potential; CT C/A/P: CT scan chest, abdomen and pelvis
 
Toxicity 30 day f/u can happen 30 days (+/- 2 weeks) after last treatment dose and this can be done by phone call.
 
Note after one year of follow-up without recurrence schedule of follow-ups can be adjusted according to standard of care. This will take precedence over the study calendar.
												

Table 10.3 Post-Resection Study Calender for Cohorts (B and C)

TIME PERIOD	Post-operative evaluation	Wk	Wk	Comment							
	1 (same day as Durvalumab)	3	5	7	9	11	13	15	every 4 months		
	(0.5-2wks post surgery)	+/-3d	+/-6 weeks								
PROCEDURE											
Durvalumab		X		X		X		X			
Oleclumab (cohort B)		X	X	X	X	X	X	X			If patient requires >12 weeks for postop recovery, they will not be initiated on adjuvant immunotherapy
Monalizumab (cohort C)		X		X		X		X			
Clinic Visit		X	X	X	X	X	X	X	X		
Physical Examination		X	X	X	X	X	X	X	X		
Vital Signs		X	X	X	X	X	X	X	X		Including BP, HR,

										temperature
Review of Concomitant Medication		X	X	X	X	X	X	X	X	
Laboratory		X	X	X	X	X	X	X	X	CBC w/differential and platelet count, LFTs (ALT, AST, total bilirubin, alkaline phosphatase), BUN or serum urea level, creatinine, Ca, Mg, Na, K, Cl, glucose)
CEA	X								X	X
TSH/FT4	X			X		X		X		
Lipase/amylase	X									
Immunogenicity Assessments, Peripheral Blood	X			X				X		X (at first visit only)

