13.3 Interim Monitoring

A Bayesian sequential monitoring design[66, 67] will be used to monitor the trial for surgery and toxicity rates. Generally, interim analyses will begin after 3 patients become evaluable, and will then be performed continuously to ensure that patients are exhibiting reasonable toxicity and surgery rates to continue the trial. Specific rules are in each subsection below. Since 1-2 patients are expected to be enrolled each month, monitoring data will be kept up-to-date and the tables below checked prior to consenting each patient once the 3rd patient in each cohort has been on study 4 weeks after the first dose of Durvalumab. Enrollment will not need to wait for the previous patient to become evaluable, but the rules will be checked for all evaluable patients before consenting each patient. This includes a risk of 1-2 patients entering on the study beyond the designed stopping rules, which is considered a reasonable risk. If accrual occurs faster than 1-2 patients per month, this practice will be reconsidered. All calculations for stopping boundaries and operating characteristics were performed in Multicenter Lean Desktop v2.1.

Patients will be evaluable once they have received the first dose of Durvalumab/tremelimumab, durvalumab/oleclumab or durvalumab/monalizumab and have then had 8 weeks time to go to surgery. If surgery has not occurred by 8 weeks then for monitoring these patients will have been considered not to have gone to surgery even if they do after 8 weeks. Patients will be allowed up to 12 weeks to complete surgical resection. If surgical resection is not done within 12 weeks from then patient will be removed from clinical trial

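### A patient whose pre-operative visit slips past day 28 can be counted as TOX-free at 4 weeks with no scheduled post-dose AE or laboratory assessment

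*Combined protocol and SAP*

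**What the plan says.** - **Denominator (13.3.2).** A patient enters the toxicity count when "evaluable (have TOX or completed 4 weeks after first Durvalumab dose without TOX".
- **Event window (13.3.2).** A TOX must "occur between the first dose of Durvalumab and surgery (or 4 weeks after that dose if the patient does not receive surgery as scheduled".
- **Exception (13.3.2).** For some grade 3 events the plan adds a condition; those "potentially treatable with steroids will only count as an extreme toxicity if it does not improve to grade 2 or better within 2 weeks".
- **Timing of checks (13.3).** The boundaries are consulted before each consent, "once the 3rd patient in each cohort has been on study 4 weeks after the first dose of Durvalumab".
- **Schedule (Table 10.1).** There are three time columns: Screening, Wk 1 (dosing) and Wk 4, the last with a printed window of 3 to 10 weeks. The AE row reads "Adverse Events Assessment X X Per CTCAE v4.03 for Cohort A and v5.0 for Cohorts B and C"; the two marks fall under Screening and Wk 4, and Wk 1 is blank. Chemistry is marked in all three columns, so the only draw after the dosing visit and before surgery is the Wk 4 one. The footnote to that column says "an allowance of 3 - 10 weeks after the administration of neoadjuvant therapy will be permitted to complete metastatic and/or primary resection".
- **Later updating (13.4).** Each summary report must bring the futility information on earlier patients up to week eight. Nothing equivalent is stated for toxicity.

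**The concern.** The rule credits absence of toxicity by the calendar, while the only scheduled look at the patient moves with the operation. If the visit falls in weeks 5 to 10, the patient passes the 4-week mark and enters the denominator as a non-event before any scheduled AE question or blood draw. Silence is then read as a negative result.

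This rule governs stopping in each cohort. The operating characteristics printed in 13.3.2 treat every patient's TOX status as known at entry to the denominator. If some negatives are really unknowns, the rule stops less often than the table says, and the errors all run in the direction of continuing.

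**Working it through.** **1. Schedule against rule**

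| Case | Scheduled AE and chemistry after dosing | Enters denominator as free of TOX |
|---|---|---|
| Surgery at about 3 weeks, as planned in 5.1 | Pre-operative visit, before day 28 | Day 28, after assessment |
| Pre-operative visit in weeks 5 to 10 | After day 28 | Day 28, before any scheduled assessment |

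The toxicity contact noted under Tables 10.2 and 10.3 does not fill the gap: "Toxicity 30 day f/u can happen 30 days (+/- 2 weeks) after last treatment dose and this can be done by phone call". It belongs to the post-resection calendars, may fall as early as day 30 − 14 = 16, and a phone call cannot show a laboratory abnormality. The post-surgery rule in 13.3.3 also uses a 4-week mark, but there the calendars have fixed-week AE and laboratory visits with windows of days.

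**2. What happens to an event found late**

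- If surgery is not as scheduled, the TOX window closes 4 weeks after the dose. An abnormality first measured at week 6 to 10 may have no datable onset before week 4 and may not count.
- If the patient is regarded as still on schedule, the window runs to surgery but the denominator has already closed at 4 weeks, and 13.4 states no toxicity update.
- A steroid-treatable grade 3 event starting after day 14 cannot complete its 2-week improvement check by day 28 (14 + 14 = 28), so its status is still open then.

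**3. Reproducing the plan's figures**

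Inputs from 13.3.1 and 13.3.2: TOX prior Beta(0.6, 1.4), reference rate 0.30; surgery prior Beta(1.2, 0.8), reference rate 0.60; cut-off 0.90; maximum 25 (Cohort A) or 15 (B, C); independent outcomes.

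With x TOX and s surgeries among n patients, stop if P(Beta(0.6 + x, 1.4 + n − x) > 0.30) > 0.90 or P(Beta(1.2 + s, 0.8 + n − s) < 0.60) > 0.90. An exact recursion over (x, s), checking after each patient from n = 3 and not at the maximum, gives at surgery rate 0.80:

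| True toxicity | A: computed / printed | B, C: computed / printed |
|---|---|---|
| 0.30 | 0.266 / 0.27 | 0.223 / 0.22 |
| 0.40 | 0.585 / 0.59 | 0.470 / 0.47 |
| 0.50 | 0.859 / 0.86 | 0.729 / 0.73 |

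All 40 printed stopping probabilities agree within 0.01.

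**4. One patient can change the decision**

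- 4 TOX of 7: P(Beta(4.6, 4.4) > 0.30) = 0.901, stop.
- One of the four recorded as no TOX, 3 of 7: P(Beta(3.6, 5.4) > 0.30) = 0.717, continue.
- 4 TOX among 7 assessed patients plus one unassessed patient credited as negative, 4 of 8: P(Beta(4.6, 5.4) > 0.30) = 0.846, continue.

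**5. Illustration of unseen TOX**

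If a share m of TOX patients is recorded as no TOX, the rule sees the rate p(1 − m). With p = 0.40 and surgery 0.80:

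| m (assumed) | Rate seen | Pr(stop early), A | Pr(stop early), B and C |
|---|---|---|---|
| 0 | 0.40 | 0.59 | 0.47 |
| 10% | 0.40 × 0.90 = 0.36 | 0.45 | 0.36 |
| 25% | 0.40 × 0.75 = 0.30 | 0.27 | 0.22 |

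The 25% row can be read from the plan's own table at toxicity 0.30.

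**6. If every event is found and counted, only late**

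The longest delay is 10 − 4 = 6 weeks, about 1.4 months. At the 1 to 2 patients per month in 13.3, that is 1.4 to 2.8 further patients.

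**The case against.** Much can be said for the plan, and most of it narrows the point.

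- **On-schedule patients are assessed.** Section 5.1 plans resection at about 3 weeks. A reader might infer that patients in general enter the denominator unassessed; the documents support this only for visits after day 28.
- **Unscheduled reporting continues.** AEs are collected from consent (7.4.1) and SAEs are reported as they arise (7.5), so symptomatic events should surface. This stands. It does not cover a silent laboratory abnormality.
- **The footnote speaks of resection.** A safety visit at nominal week 4, separate from the operation, is a possible reading. But the printed window applies to the whole column, and the ambiguity itself needs settling.
- **Delay does not imply hidden toxicity.** A reader might infer that delayed patients, for whom the window was widened because of immune-mediated events, are the likeliest to hide a TOX. If such an event caused the delay, it had already been detected. Those delayed for other reasons are the ones without an assessment, and nothing shows that they carry excess toxicity.
- **The reported events are not a TOX count.** Section 2.6 states "Grade 3/4 reported toxicities were fatigue (n=1), thromboembolic event (n=1), lipase elevation (n=1) and AST/ALT increase (n=3". A reader might take four of six as TOX visible only in blood, or 3 of 18 − 2 = 16 treated patients (19%) as a TOX rate. Section 13.3.2 excludes asymptomatic lipase elevation, AST/ALT events may fall under the steroid exception, and 2.6 gives neither their course nor their timing. The list shows only that blood draws matter here.
- **Large unseen shares need much delay.** Even with a laboratory share of 4/6 and no unscheduled detection, 25% unseen requires 0.25 ÷ (4/6) = 38% of TOX patients to be seen after day 28; 10% unseen requires 0.10 ÷ (4/6) = 15%.
- **Late events may enter later checks.** Section 13.3 wants monitoring data current and already accepts 1 to 2 patients beyond a boundary. That helps if the event is still countable, which the 4-week window and the missing toxicity update leave open.
- **The final AE tabulation in 13.4 does not depend on the 4-week mark.** This stands; the weakness lies in interim monitoring.

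**Conclusion.** The point holds in a limited form. Followed as written, 13.3.2 and Table 10.1 allow a patient whose pre-operative visit falls after day 28 to count as evaluable and free of TOX with no scheduled post-dose AE or laboratory assessment. The exposure is mainly to laboratory-only toxicity such as AST/ALT increases, and an event first found after week 4 may then fall outside the window.

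The effect size is unknown, because the documents give neither the share of delayed visits nor the share of events missed. The falls from 0.47 to 0.36 or 0.22 (Cohorts B and C) and from 0.59 to 0.45 or 0.27 (Cohort A) rest on assumed unseen shares of 10% and 25% and on permanent misclassification. They show sensitivity and do not estimate bias. The Cohort A figures matter less, since 13.2 expects that cohort to be about fully enrolled when this revision is approved. The change should be made as a cheap improvement to a stopping rule; the finding does not invalidate the design.

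**What to change.** 1. **13.3.2:** count a patient as evaluable without TOX only when an AE assessment and the Table 10.1 chemistry are recorded on or after day 28 from the first durvalumab dose, or at the pre-operative visit if surgery is earlier.
2. **Table 10.1:** separate the week-4 safety assessment (AE and laboratory, with its own fixed window) from the resection visit with its 3 to 10 week allowance.
3. **13.4:** at each summary report, update the toxicity status of earlier patients as well as their futility status. This also picks up events whose 2-week improvement check was still open at week 4.

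The cost is a short amendment and, for patients with delayed surgery only, one routine blood draw and AE check, or a slightly later entry into the denominator. Patients operated on at about 3 weeks need nothing extra. The priors, boundaries and printed operating characteristics need no change for this point.
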